The primary objective of this study is to address critical safety questions with concurrent TDF-based PrEP and DMPA use. We hypothesize that young women using TDF-based PrEP and DMPA will have lower bone acquisition and altered bone metabolism. Bone mineral metabolism is in part regulated by the kidney, and we hypothesize that bone effects from concurrent PrEP and DMPA use will be driven by subclinical kidney injury, a known side effect of TDF, as well as DMPA-induced hypoestrogenism. To investigate our hypothesis, we will enroll a prospective cohort of approximately 500 HIV-uninfected women ages 16-25 years in Kampala, Uganda who have substantial HIV risk and are initiating DMPA or barrier method contraception. Over a 24-month period, we will offer TDF-based PrEP. We will use state-of-the-art radiologic, biochemical, and epidemiologic methods to test the hypothesis that concurrent TDF-based PrEP and DMPA use results in compounding adverse effects on bone health.

II. BACKGROUND

PrEP as a novel HIV prevention strategy for women

Women in sub-Saharan Africa are disproportionately affected by HIV and the greatest rates of HIV incidence are among women below age 25. In Uganda, 4% of young women were estimated to be living with HIV and 140,000 people became infected in 2013.¹ For women with substantial HIV risk, tenofovir disoproxil fumarate (TDF)-based pre-exposure prophylaxis (PrEP) is a daily oral medication highly protective against HIV acquisition.²⁻⁷ Randomized trials of PrEP efficacy demonstrated high HIV protection at levels >90% in analyses of participants with high adherence.⁴⁻⁷ Recent landmark approvals of TDF-based PrEP in sub-Saharan Africa and commitment from large-scale funding partners (including PEPFAR) will accelerate its roll-out.⁸ WHO antiretroviral guidelines now include PrEP and clinical guidelines for Uganda are under development. A key advantage of PrEP for women is that it does not require the cooperation of a male partner, a challenging characteristic of condom use. Although two trials of PrEP conducted with African women showed null results, there is substantial objective evidence indicating that these studies were limited by low adherence to study medication.^{3, 9, 10} Concerns about PrEP adherence by young women have been abated by data from PrEP delivery studies demonstrating very high adherence with open-label products with known efficacy and accompanied by risk-related counseling.¹¹

Unintended consequences of PrEP

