Subclinical kidney injury is characterized by isolated abnormalities in some of markers of kidney function, but without generalized clinical disease manifestation. Kidney toxicity can result in phosphate wasting with hypophosphatemia and secondary hyperparathyroidism, leading to dysregulation of calcium-phosphate homeostasis and bone demineralization.^{24-29, 33} Higher tenofovir plasma concentrations have been associated with higher vitamin D binding protein, lower 1,25-OH(2)D, lower estimated free 25-OHD, and increased parathyroid hormone (PTH) in HIV-infected persons. Vitamin D ensures a proper balance of calcium and phosphorus, key minerals for bone metabolism (Figure 2).^{26, 27}

Our research has recently shown that TDF-based PrEP is associated with a small decline in estimated glomerular filtration rate (eGFR) in African men and women (Table 2).³⁴⁻³⁶ It is not known whether this low level of kidney injury will be exacerbated with prolonged use of TDF-based PrEP or in women with small body mass. Studies are needed to address the effect of

concurrent use of DMPA and TDF-based PrEP on bone acquisition in young women who have generally small body structures that potentially elevate their risk for TDF-induced BMD decline and kidney injury.

Effects of DMPA on bone density

The most commonly used contraception in sub-Saharan Africa is DMPA, used by more than half of contracepting women in Uganda (Figure 3).³⁷

[figure not shown]
⁴⁰ Intramuscular 150mg DMPA is often preferred because of it is easy to administer and can be used discretely. Intramuscular DMPA, as well as a lower dose subcutaneous formulation, is known to yield BMD loss to such an extent as to warrant a “black box” warning from the U.S. Food and Drug Administration.^{38, 41-48} Since 2012, a global partnership of >50 governments, private sector, and multi-lateral organizations has made huge efforts to increase access to subcutaneous DMPA, implying that DMPA will remain the predominant contraceptive in this setting for the foreseeable future.⁴⁸ Women currently using DMPA have a lower average BMD than non-users and these effects are more pronounced in younger women.^{41, 43, 44, 46, 49-51} Longitudinal studies have reported BMD losses up to 7.5% of BMD after ≥ 2 years of use (Table 3) and the greatest amount of loss during the first 1-2 years.⁴⁴

Effects of DMPA on bone metabolism

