For young women who equally need TDF-based PrEP to prevent HIV infection and effective contraception to prevent unintended pregnancy, concerns about TDF-induced reductions in bone mass and associated kidney injury must be heightened. Both are known to have minor effects on bone density and bone metabolic markers but through separate pathways. However, it is unknown if there is a joint effect of concurrent use of PrEP and DMPA on bone density and markers of bone metabolism and whether there are any cross-pathway effects that would result in clinically relevant changes to young women's bone health. This risk is particularly salient for women below age 25 who have not yet acquired peak bone mass and thus studying the effects of concurrent PrEP and DMPA use on bone health in this population is especially paramount.

Public health impact

[figure not shown]
This study will provide the first opportunity to evaluate reductions in bone mass and the preceding mechanisms triggered by the simultaneous initiation of PrEP and DMPA during a critical time of bone maturation in a cohort of young women. As PrEP delivery is brought to scale in multiple African settings where young women are a predominant risk population and DMPA use is widespread and will remain common, safety findings from our study will address a key knowledge gap and be pertinent to recommendations about concurrent use and how to best incorporate PrEP into the lives of young women.

III. STUDY METHODS

Overall Design

The proposed research will investigate the hypothesis that TDF-based PrEP and DMPA initiated concurrently by HIV-uninfected women will enhance each other's effects on bone metabolism. We will conduct an open-label prospective study of approximately 500 HIV-uninfected women at substantial risk for HIV-infection who are newly initiating DMPA or using condoms as their only contraceptive in Kampala, Uganda (Figure 5). We will offer PrEP to all of these women and determine the joint effect of PrEP and DMPA on changes in bone mass (Aim 1), bone turnover, subclinical kidney injury, and hypoestrogenism (Aim 2), and conduct mediation analysis to assess the contribution of each pathway to overall losses in bone mass (Aim 3).

Aims

1. We will assess whether young women using TDF-based PrEP and DMPA concurrently attain lower peak bone mass over a 24-month period and have evidence of disrupted microarchitecture, relative to women using either agent singly or neither agent

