Kidney function will be monitored 6 months after initiation and annually thereafter, in accordance with Ugandan guidelines, using creatinine clearance calculated by Cockroft–Gault equation. DXA scans will be reviewed in real time and women with bone density below -2.0 standard deviation of the z-score will be referred locally for vitamin D assessment and provided with any necessary therapy. The investigators will be responsible for continuous close monitoring of all adverse events that occur among study participants. For the purposes of this study, only serious adverse events (SAEs) and adverse events felt related to PrEP will be documented on case report forms. Adverse events and the severity of clinical symptoms will be scored using the DAIDS Table for Grading the Severity of Adult and Pediatric AEs.⁶² The study safety monitor will review clinical and laboratory SAEs in real time as they are reported by the site clinicians on CRFs and through email within 48 hours of occurrence. As needed, the safety monitor will work provide rapid consultation with clinicians regarding the management of toxicities. A Safety Review Team comprised of the study investigators and lead clinicians will review clinical and laboratory safety reports summarizing SAEs via conference call on an approximately quarterly basis.

IV. DATA COLLECTION

Clinical data including anthropometric, dietary, physical activity and other lifestyle and sexual behaviors, will be recorded electronically on case report forms (CRFs) and data will be uploaded to a secure server. Automated legal range checks will be programmed to reduce data entry errors and internal quality control reports will be run on a monthly basis. Results from laboratory testing will be returned to the data center at the University of Washington and stored alongside other key study data. DXA scan images will be downloaded to project-specific databases and sent to the University of Washington via secure file transfer system. TBS measurements will be performed using the lumbar spine DXA images. PrEP adherence data from the electronic monitoring device will be stored on an encrypted website and downloaded to the University of Washington server on a regular basis.

V. DATA ANALYSIS

Aim 1. We will assess whether young women using TDF-based PrEP and DMPA concurrently attain lower peak bone mass over a 24-month period and have evidence of disrupted microarchitecture, relative to women using either agent singly or neither agent

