An independent Data Monitoring Committee will be established to protect patient safety by monitoring study outcomes, implementation, and data quality. The committee will consist of expert clinicians, statisticians, and scientists, including Ugandans, in the field of PrEP and family planning delivery in sub-Saharan African settings. The committee will meet via teleconference every 6 months and be charged with the decision to recommend stopping the study early if interim analyses yield any safety concerns. In addition, the committee will provide guidance about results from international studies of PrEP and contraception that may spur Ugandan policy change. Reports from all reviews will be submitted to overseeing institutional review boards and ethics committees.

Informed consent

We will perform paper-based or electronic-based consenting of participants. After we have ensured that participants have read and understood the consent forms, we will ask them to append their signature on a tablet or on paper. Each participant will receive a participant information sheet that they can use for reference. However, any participant who wants their consent form to take home will have it printed and given to them. Using electronic-based consenting will greatly reduce the burden of storing paper-based consent forms.

Risks

Risks for this cohort include side effects from PrEP provided to the young women through the study clinic, DMPA and other contraceptives provided through Ugandan public health clinics according to the national guidelines for contraceptive provision in Uganda, and discomfort associated with blood draws, physical exams, interviews, and HIV counseling and testing. Intensive and ongoing counseling and monitoring of side effects and adverse events limit the risk for participants from the direct study procedures. Women will have three DXA scans during the course of the study and be exposed to radiation during each scan. The effective radiation dose from the DXA procedure, approximately 0.01 millisievert (mSv), is similar to that received during a 5-hour airplane flight. The total dose over these 3 scans will be several orders of magnitude less than the radiation exposure women will have from their natural environments (from sources such as sun, air, food, and soil). Women who become pregnant will not undergo DXA scans.

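### Non-serious adverse events are documented only when attributed to PrEP with exposure known, so they cannot be compared between exposure groups, and DMPA-related ones outside the measured outcomes go unrecorded

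*Protocol*

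**What the plan says.** The opening summary of the protocol sets the aim: "The primary objective of this study is to address critical safety questions with concurrent TDF-based PrEP and DMPA use". Overall Design fixes the setting: "We will conduct an open-label prospective study of approximately 500 HIV-uninfected women". Under Contraceptive provision, the study takes over DMPA injections during follow-up. The Risks subsection of Section VI lists side effects of both PrEP and DMPA.

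The Safety monitoring subsection of Section III gives three rules:

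- **Monitoring:** "The investigators will be responsible for continuous close monitoring of all adverse events that occur among study participants".
- **Documentation:** "only serious adverse events (SAEs) and adverse events felt related to PrEP will be documented on case report forms".
- **Review:** "The study safety monitor will review clinical and laboratory SAEs in real time", and the Safety Review Team "will review clinical and laboratory safety reports summarizing SAEs via conference call on an approximately quarterly basis".

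Separately, the Study oversight subsection of Section VI sets up an independent Data Monitoring Committee. It meets every six months, and its remit is not restricted to serious events.

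**The concern.** Two agents are under study, but the rule for non-serious events refers to one of them. Whether an event is recorded depends on a causal judgment by someone who knows what the woman is taking. In women who have never used PrEP the judgment can go only one way. In concurrent users it asks the clinician to attribute an event to one of two drugs that the Background section says may act additively or synergistically.

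Two things are at stake. First, a tabulation of documented non-serious events by exposure group, whether for the Data Monitoring Committee or in the final report, would show an excess on PrEP that the recording rule produces by itself. It could not show whether adding PrEP to DMPA adds harm. Second, non-serious DMPA effects with no outcome measure of their own leave no adverse event record. A later statistical analysis plan cannot repair either problem, because the data will not have been collected.

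**Working it through.** The protocol states no figure on this point to reproduce. The check sets its provisions side by side and then counts who falls under the rule.

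**Step 1. What the rule documents, by exposure.** Serious events are documented in every group. For non-serious events:

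| Group | Attributed to PrEP | Attributed to DMPA | Attributed to neither |
|---|---|---|---|
| PrEP + DMPA | documented | not documented | not documented |
| PrEP only | documented | not applicable | not documented |
| DMPA only | cannot arise | not documented | not documented |
| Neither | cannot arise | not applicable | not documented |

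The Risks subsection describes contraceptives as coming through public clinics, whereas Contraceptive provision has the study taking them over. On either reading DMPA is one of the two exposures under study, so the table stands.

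**Step 2. How many women.** Sample size and study power gives 300 DMPA users, 200 condom users and 75% uptake among DMPA users. No uptake is given for condom users, so the same rate is assumed for them.

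- DMPA without PrEP: 300 × 0.25 = 75 (the protocol's own figure).
- Condoms without PrEP: 200 × 0.25 = 50 (assumption).
- Total: (75 + 50) / 500 = 25%.
- At 90% uptake: 30 + 20 = 50 of 500 (10%).
- At 50% uptake: 150 + 100 = 250 of 500 (50%).

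**Step 3. Illustration of the artefact (assumed rates).** Take a true risk of a non-serious event of 10% in both DMPA groups, with half of the events in PrEP users attributed to PrEP.

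- PrEP + DMPA: 225 × 0.10 × 0.5 = 11.25, so about 11 of 225 documented (5%).
- DMPA only: 75 × 0.10 = 7.5 true events, 0 of 75 documented (0%).

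The true difference is zero. The documented difference of 5 percentage points comes wholly from the rule.

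**Step 4. Who reviews what is documented.** In Safety monitoring, both the safety monitor's real-time review and the Safety Review Team's quarterly report are described in terms of serious events. A documented non-serious event attributed to PrEP therefore has no periodic reviewer named in that subsection. Investigators do have a general monitoring duty, and the safety monitor can be consulted on toxicities.

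**Step 5. What is collected outside the adverse event form.** These items do not depend on attribution:

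- Fractures: asked at every visit in the medical history questionnaire.
- Bone density: DXA at enrollment, 12 and 24 months unless pregnant, reviewed in real time.
- Kidney, bone turnover and estrogen markers: blood and urine archived quarterly, with markers measured at baseline, 3, 6, 12 and 24 months. Women without TDF exposure are the kidney comparator in Aim 2, part 2.
- Amenorrhea: from the menstrual cycle questionnaire.

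One asymmetry remains. The visit table schedules creatinine after screening only for women using PrEP, and archived samples are batch-analyzed. Women off PrEP therefore have no scheduled real-time kidney result. This matters because the Background says: "Subclinical kidney injury is characterized by isolated abnormalities in some of markers of kidney function, but without generalized clinical disease manifestation". Such changes are found by testing rather than by symptoms.

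**The case against.** The strongest reply is that the safety questions of this study are bone, kidney and estrogen effects, and that these are measured in every woman as outcomes. On that reading the adverse event form is a secondary channel, no listed analysis uses non-serious events, and reduced collection is a reasonable economy for marketed drugs. Serious DMPA events are still documented whatever their cause. Most of this stands. It is why the point does not touch Aims 1 to 3 and why reduced collection should stay.

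The Risks subsection might be read as contradicting the rule, since it says: "Intensive and ongoing counseling and monitoring of side effects and adverse events limit the risk for participants from the direct study procedures". It does not. That sentence promises counseling and monitoring, not case report form entries, and it concerns risk from study procedures.

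A reader might also infer that kidney and bone events in women off PrEP are lost, or that nobody looks beyond serious events. The protocol supports neither reading. The collection listed in the last step of the working covers all women, low bone density z-scores trigger referral, and the Data Monitoring Committee's remit includes study outcomes.

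What the reply does not answer is that the rule is written around one of two study drugs. Any non-serious event data that reach the committee carry the asymmetry with them, and non-serious DMPA events outside the measured outcomes are recorded nowhere as adverse events.

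**Conclusion.** The point holds as a limited defect in adverse event documentation and review. Documented non-serious events cannot be compared between exposure groups. The 75 DMPA-only women expected at 75% uptake can have none, nor can about 125 of 500 women in all if condom users have the same uptake (50 to 250 across uptake of 90% to 50%). These are counts of women under the rule who have not taken PrEP, not estimates of missed events. The 5% versus 0% contrast rests on assumed rates and only shows the mechanism. Non-serious DMPA-related events outside the measured outcomes are not documented, and documented non-serious PrEP-related events have no named periodic reviewer in Safety monitoring.

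The protocol does not support the stronger conclusion that the primary or secondary comparisons are biased by this rule. They rest on DXA, laboratory markers and questionnaires collected without regard to attribution. The change is worth making because it is cheap, because it alters a rule the protocol states outright, and because omitted records cannot be recovered later.

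**What to change.** In the Safety monitoring subsection:

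1. Keep reduced collection, but document non-serious events attributed to PrEP or to DMPA.
2. Document fractures in all women regardless of attribution. Do the same for creatinine abnormalities graded by the DAIDS table, wherever a result exists.
3. Extend the quarterly Safety Review Team report, and any adverse event table given to the Data Monitoring Committee, to these events, tabulated by current exposure group.
4. State in those reports that events recorded by attribution, and creatinine events, are not comparable between PrEP users and non-users, since scheduled real-time creatinine after screening applies only during PrEP use. Refer kidney comparisons to the archived samples, which are collected alike in all groups.

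No new testing is required. The cost is some additional case report form entries and one more table in an existing report. Fractures are already asked about at each visit. The change does not make creatinine ascertainment equal between groups, which is why the caution in item 4 is needed.

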We will use dual energy x-ray absorptiometry (DXA) scans to measure BMD annually at 3 anatomical sites (lumbar spine, total hip, and wrist). Additionally, we will derive the trabecular bone score (TBS), an index of lumbar spine trabecular microarchitecture.

Hypothesis: Relative to women using DMPA only (without tenofovir exposure) and women using PrEP only (without DMPA exposure), women concurrently using TDF-based PrEP and DMPA will have lower bone mass and more disruptions in bone microarchitecture.

2. We will investigate whether young women concurrently using TDF-based PrEP and DMPA experience: 1) higher rates of bone turnover, a direct precursor to bone loss and 2) subclinical kidney injury and hypoestrogenism, markers of two mechanistic pathways between TDF and DMPA use and bone mass

At baseline, 3, 6, 12, and 24 months, we will measure:

- 1) Markers of bone formation and resorption (e.g. NTX, P1NP, serum intact parathyroid hormone, total and bioavailable 25-OH-vitamin D)
- 2) Markers of kidney function (phosphate, glucose, creatinine, total protein, albumin) and
- 3) Markers of estrogen (serum estradiol, sex hormone binding protein, and the occurrence of amenorrhea)

Hypothesis: Relative to women using DMPA only and PrEP only, women concurrently using TDF-based PrEP and DMPA will have increased bone turnover markers and PTH. In addition, women concurrently using TDF-based PrEP and DMPA will have more frequent subclinical kidney injury (relative to women without tenofovir exposure) and reduced serum estrogen (relative to women without DMPA exposure).

3. Using mediation analysis, we will identify the degree to which the pathways through subclinical kidney injury and hypoestrogenism account for changes in bone density among women concurrently using TDF-based PrEP and DMPA

We will conduct mediation analysis to determine the degree to which changes in the pathways through subclinical kidney injury, hypoestrogenism and the combination of these pathways account for changes in bone density.

Hypothesis: The pathway through hypoestrogenism will be a stronger link between concurrent TDF-based PrEP and DMPA use and bone density changes.

Population

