- Current or recent history of primary or secondary amenorrhea
- Taking medications known to interfere with bone metabolism (steroids, anti-convulsants, bisphosphonates, cancer drugs).
- Has any other condition that would preclude the ability to provide informed consent, make study participation unsafe, complicate the interpretation of study findings or otherwise interfere with achievement of the study objectives, in the investigator's discretion.

Sample size and study power

Power calculations are based on the number of participants needed to achieve aim 1. Our target sample size is 500 women, of which 300 will be using DMPA and 200 will be using condoms for contraception. We calculate that with 300 women newly initiating DMPA and 75% of women choosing to initiate PrEP, thus with 225 women concurrently using PrEP and DMPA and 75 women using DMPA without PrEP, we will have >90% power to detect changes as low as 2.2% in BMD (with 1.0 g/cm² mean BMD loss) at any anatomical site between women using PrEP and DMPA concurrently and women using DMPA only during the 24 month follow up period (Table 4). Should more than 90% of women choose to initiate PrEP (270 women concurrently using PrEP and DMPA and 30 women using DMPA without PrEP), we will have 80% power to detect changes of >2.7% or more and should initiation rates be closer to 50% (150 women concurrently using DMPA and PrEP and 150 women using DMPA without PrEP), we will have >90% power for all comparisons.

Table 4. Power calculations. N=500: 300 on DMPA and 200 on condoms, shown with a range of PrEP acceptance for the primary comparison of DMPA + PrEP vs DMPA ($\alpha=0.05$)

Expected PrEP acceptance	Outcome: BMD (Aim 1)			Outcome: NTX (Aim 2)		
	Mean % Δ (std dev range)	Mean Δ	Power	Mean % Δ	Mean Δ	Power
75% (225 DMPA+PrEP, 75 DMPA)	2.2 (4–5) (0.5–1.0)	0.5 (0.5–1.0)	91%	2.2 (4–5)	0.10 (0.2 – 0.5)	>99%
75% (225 DMPA+PrEP, 75 DMPA)	2.5 (4–5) (0.5–1.0)	0.5 (0.5–1.0)	>96%	2.5 (4–5)	0.20 (0.2 – 0.5)	>96%
75% (225 DMPA+PrEP, 75 DMPA)	3 (4–5) (0.5–1.0)	1.0 (0.5–1.0)	>99%	3 (4–5)	0.50 (0.2 – 0.5)	>99%
90% (270 DMPA+PrEP, 30 PrEP)	2.5 (4–5) (0.5–1.0)	0.5 (0.5–1.0)	74-90%	2.5 (4–5)	0.10 (0.2 – 0.5)	>99%

Recruitment

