Recruitment strategies will include collaboration with local family planning clinics, gynecologists, women's health clinics, HIV counseling and testing centers, and public and private health clinics. Additionally, we will conduct outreach activities during community markets to recruit women newly initiating contraception. Recruitment materials will educate women about the benefits and potential adverse effects of contraceptives and PrEP, based on available data.

General study procedures

Over a 24-month period, we will follow women quarterly with HIV rapid testing, PrEP adherence counseling and refills, DMPA injections, and provision of other contraceptives as desired. At enrollment and quarterly visits, we will assess physical activity, sexual behavior, and menstrual cycle characteristics. Annually, we will conduct physical exams and anthropometric readings. Sexually transmitted infections will be routinely assessed syndromically, according to national guidelines. Women will be encouraged to consider their HIV risk and fertility desires at every visit and counseled about contraception and PrEP accordingly. Dual energy x-ray absorptiometry (DXA) scans will be performed at baseline and annually thereafter. Blood and urine samples will be obtained quarterly, aliquoted, and archived at minus 80° Celsius.

DXA and TBS assessments

DXA scans will be conducted at study enrollment (within 1 week of contraceptive initiation if possible), 12, and 24 months after enrollment. DXA is the clinical standard for measuring BMD. It is painless and non-invasive. Women will be exposed to a relatively low level of radiation which is <1/10 the dose of a standard chest x-ray, and less than a day's exposure to natural radiation. BMD by DXA of the hip and spine is generally considered the most reliable way to classify osteoporosis, assess changes in BMD, and predict fracture risk. We will measure areal BMD of the lumbar spine (L1-4), hip, whole body and body composition (total and % fat and lean mass) using a DXA machine. For the TBS analysis, no additional image acquisition is required. TBS will be performed as a re-analysis of the lumbar spine taken as part of the standard DXA procedure with specialized software.

Contraceptive provision

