The primary analysis will be separate comparisons of the annualized rates of change in BMD and TBS of the spine and hip between women using PrEP and DMPA concurrently versus women using DMPA only (comparison 1), women using PrEP only (comparison 2), and women using neither (comparison 3). Analyses will account for baseline BMD.

Aim 2, part 1. We will investigate whether young women concurrently using TDF-based PrEP and DMPA experience higher rates of bone turnover relative to women using either agent singly or neither agent

This outcome will be defined by the percent change from baseline of serum levels of NTX and P1NP over 24 months. Secondary outcomes will include: 1) percent change from baseline in serum levels of intact PTH, total 25-(OH)D, bioavailable (i.e. unbound or free) 25-(OH)D calculated from vitamin D binding protein (VDBP) using the standard equation.

$$\text{Free 25(OH)D} = \frac{\text{total 25(OH)D}}{1 + (6 \times 10^3 \times \text{albumin}) + (7 \times 10^8 \times \text{DBP})}$$

To test the hypothesis that combined PrEP and DMPA use is associated with greater bone turnover than DMPA use alone, we will use time-dependent linear mixed-effects regression models to compare mean percent changes in NTX and P1NP between concurrent users of PrEP and DMPA versus users of DMPA only. Secondary powered comparisons will be between: a) concurrent users of PrEP and DMPA versus users of PrEP only; b) users of PrEP only versus users of condoms only; c) users of DMPA only vs users of condoms only. Analysis of the percent change from baseline in serum levels of intact PTH, total 25-OH-D and bioavailable 25-OH-D over 24 months will follow a similar approach. All analyses will be adjusted for confounders and we will consider a broad range of demographic, medical, lifestyle, and sexual behavior characteristics as potential confounders.

Aim 2, part 2. We will investigate whether young women concurrently using TDF-based PrEP and DMPA experience elevated markers of subclinical kidney injury relative to women using TDF-based PrEP alone

This outcome will be defined as having either:

- 1) eGFR decline ($\geq 25\%$ decline from baseline or creatinine clearance $< 60 \text{ mL/min}$). GFR will be calculated using the Chronic Kidney Disease Epidemiology (CKDE) collaboration equation

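### The Aim 1 primary analysis should place TBS at the lumbar spine only and tie it to its own baseline; as worded it covers spine and hip and names only baseline BMD

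*Protocol*

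**What the plan says.** Under V. Data Analysis, Aim 1, the primary analysis consists of "separate comparisons of the annualized rates of change in BMD and TBS of the spine and hip". Concurrent users of PrEP and DMPA are compared in turn with users of DMPA only, users of PrEP only, and users of neither. The next sentence is the whole provision for baseline values: "Analyses will account for baseline BMD". It makes no separate provision for TBS, and no model form is given for Aim 1.

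Three other places say where TBS comes from:

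- III. Study Methods, Aims (Aim 1): "the trabecular bone score (TBS), an index of lumbar spine trabecular microarchitecture".
- DXA and TBS assessments: "TBS will be performed as a re-analysis of the lumbar spine taken as part of the standard DXA procedure with specialized software".
- IV. Data Collection: "TBS measurements will be performed using the lumbar spine DXA images".

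DXA scans are scheduled at enrolment, 12 months and 24 months.

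**The concern.** Two things in the sentences that define the primary analysis do not fit the rest of the protocol.

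**Site.** As written, the site phrase covers both BMD and TBS. That makes four outcome-by-site combinations, one of which (hip TBS) the described data cannot supply. A reader has to work out that three are meant.

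**Baseline value.** The protocol has already decided that the Aim 1 analyses need a baseline value. For BMD it names the natural one. For TBS it names the baseline of another variable. With change in TBS as the outcome, baseline TBS is the value most directly tied to the residual variance and to regression to the mean. The exposure groups are formed by the women's own choices about PrEP and contraception, so a baseline difference in TBS is possible. At stake are some precision for one of the two primary-analysis outcomes, and a covariate choice better fixed before results are known in an open-label cohort.

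**Working it through.** **1. The site wording, side by side.** Data Analysis attaches spine and hip to both outcomes. The Aims, the DXA and TBS assessments section and Data Collection each limit TBS to the lumbar spine, and nothing in the protocol describes a hip TBS. Read literally: 2 outcomes × 2 sites = 4 combinations, × 3 comparisons = 12. As the data allow: BMD at 2 sites + TBS at 1 = 3 combinations, × 3 comparisons = 9.

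**2. Availability of baseline TBS.** TBS needs no extra image, and the visit table has a DXA scan at enrolment. Baseline TBS therefore exists wherever baseline lumbar spine BMD does.

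**3. The protocol's own power figure, and whether it is touched.** Inputs from Sample size and study power and Table 4: "225 women concurrently using PrEP and DMPA and 75 women using DMPA without PrEP"; difference 2.2%; SD 4 to 5; alpha 0.05 (sidedness not stated, taken as two-sided).

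- SD 5: SE = 5 × √(1/225 + 1/75) = 0.667; 2.2/0.667 = 3.30; 3.30 − 1.96 = 1.34; power 0.910. This reproduces the stated 91%.
- SD 4: SE = 0.533; 2.2/0.533 = 4.125; 4.125 − 1.96 = 2.165; power 0.985.

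The calculation concerns BMD. The protocol gives no effect size, SD or correlation for TBS, so the point alters no stated number.

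**4. Precision from using baseline TBS.** Assumptions: two scans, equal variances (set to 1), and a baseline-to-follow-up TBS correlation ρ of 0.7 to 0.9, which is not in the protocol.

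- Variance of the unadjusted change: 2(1 − ρ).
- Residual variance after baseline TBS: 1 − ρ².
- Ratio of standard errors: √[(1 − ρ²) / 2(1 − ρ)] = √[(1 + ρ)/2].

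| ρ | SE ratio | Reduction in SE |
|---|---|---|
| 0.7 | 0.922 | 7.8% |
| 0.8 | 0.949 | 5.1% |
| 0.9 | 0.975 | 2.5% |

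Dividing by a fixed follow-up time to annualize leaves these ratios unchanged.

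**5. Why this is an upper limit.** The table compares against no baseline adjustment, but the protocol already accounts for baseline BMD. Suppose baseline BMD correlates r with baseline TBS and is related to TBS change only through it. BMD then already explains r²(1 − ρ)/2 of the variance of change, and the remaining ratio is √{[(1 + ρ)/2] / [1 − r²(1 − ρ)/2]}.

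- r = 0.5, ρ = 0.7: √(0.85/0.9625) = 0.940, a reduction of 6.0%.
- r = 0.5, ρ = 0.9: √(0.95/0.9875) = 0.981, a reduction of 1.9%.
- r = 0.2, ρ = 0.7: √(0.85/0.994) = 0.925, a reduction of 7.5%.

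The values of r are illustrations; the protocol gives none.

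**6. Estimated difference between groups.** If the groups differ at baseline by a gap g in TBS, the unadjusted change score and the analysis adjusted for baseline TBS differ by (1 − ρ) × g. This is a difference between two estimates. Which of them is nearer the truth depends on how the groups would have moved without exposure, and the protocol cannot settle that.

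**The case against.** **The site phrase is shorthand.** Three passages limit TBS to the lumbar spine, no hip TBS is planned, and no estimate depends on the phrase. This largely stands: taken alone, the wording is close to clerical.

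**The protocol does not exclude baseline TBS.** It says that analyses will account for baseline BMD; it does not say only BMD. Covariates are often settled in a statistical analysis plan, which is not shown here. This stands too, and rules out saying that the plan rejects baseline TBS. What remains is that the protocol did not leave the matter open: it fixed a baseline value for all Aim 1 analyses, and for TBS it is another outcome's.

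**A stronger reading.** A reader might infer that leaving out baseline TBS creates a false group difference of a calculable size. With an assumed gap of 0.2 to 0.3 SD and ρ of 0.9 to 0.7, (1 − ρ) × gap runs from 0.02 to 0.09 SD of TBS, and it is tempting to set this against the design effect. The documents do not support that:

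- The quantity is a bias only if both groups regress to a common mean. If self-selected groups have stable, different TBS levels, the unadjusted change is unbiased and adjustment introduces the same error.
- Neither the gap nor ρ is in the protocol. The formula also uses the marginal TBS correlation, which need not apply once baseline BMD is in the model.
- The only design effect available is for BMD: 2.2/5 = 0.44 SD, or 2.2/4 = 0.55 SD at the other end of the stated range. The study is not sized on TBS.

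**Conclusion.** The point holds as a small, inexpensive improvement to the definition of the primary analysis. The site wording conflicts with three other places in the protocol. The single baseline value named for the TBS comparison belongs to a different outcome, while baseline TBS is to hand and not ruled out.

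The expected gain in standard error for TBS change is at most about 2% to 8% under an assumed correlation of 0.9 to 0.7, and less with baseline BMD already in the model. Own-baseline adjustment also protects against regression to the mean if the groups differ at enrolment and would drift to a common mean. Whether any bias arises, and how large, cannot be determined from the protocol. The stated power and sample size stand as they are.

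**What to change.** In V. Data Analysis, Aim 1, change two phrases:

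- State the outcomes as *BMD of the spine and hip and TBS of the lumbar spine*.
- State the adjustment as *each analysis will account for the baseline value of its own outcome (BMD at the same site; TBS for TBS)*.

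If a statistical analysis plan exists, it should carry the same wording. Because groups are self-selected, it would help to state there why baseline adjustment is preferred to an unadjusted change. The cost is a wording change only: no new scans, data or participants, and no change to Table 4.
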